4.3 ANALYSES OF SAFETY/TOLERABILITY

As stated in the Clinical Protocol NI03-CV19-001 Version 4.0, all reported AEs will be coded using the latest version of the Medical Dictionary for Regulatory Activities (MedDRA). The incidence of Treatment Emergent Adverse Events (TEAEs) will be included in incidence tables. Events with missing onset dates will be included as treatment emergent. If a subject experiences more than 1 occurrence of the same AE, the occurrence

⁵ Kaplan EL and Meier P. Nonparametric estimation from incomplete observations, Journal of the American Statistical Association, 53:457-481, 1959.

⁶ Cox DR. Regression models with life-tables (with discussion), Journal of the Royal Statistical Society, B. 66:188-90, 1972.

with the greatest severity and the closest association with the study drug will be used in the summary tables. SAEs, Common Terminology Criteria for Adverse Events (CTCAE) grades 3, 4, or 5 TEAEs, and TEAEs causing discontinuation will be summarized using discrete summaries by system organ class and preferred term for each treatment group. All AEs will be listed by subject, along with information regarding onset (study day), duration, relationship and severity to study drug, action taken with study drug, treatment of event, and outcome.

Treatment emergent adverse events (TEAEs) are defined as all adverse events that occur after first study treatment (either active or placebo). TEAEs will be summarized by severity and relationship separately.

All adverse events that lead to death or are life threatening will be recorded as Serious Adverse Events in the SDTM datasets. Only non-COVID related Serious Adverse Event (SAE's) will be included in the summaries provided below.

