12.4 Adverse Events

12.4.1 Adverse Events

An AE is any symptom, physical sign, syndrome, or disease that either emerges during the study or, if present at screening, worsens during the study, regardless of the suspected cause of the event. All medical and psychiatric conditions (except those related to the indication under study) present at screening will be documented in the medical history eCRF. Changes in these conditions and new symptoms, physical signs, syndromes, or diseases should be noted on the AE eCRF during the rest of the study.

Subjects will be instructed to report AEs at each study visit. All AEs are to be followed up until resolution or a stable clinical endpoint is reached.

Each AE is to be documented on the eCRF with reference to date of onset, duration, frequency, severity, relationship to study drug, action taken with study drug, treatment of event, and outcome. Furthermore, each AE is to be classified as being serious or nonserious. Changes in AEs and resolution dates are to be documented on the eCRF.

For the purposes of this study, the period of observation for collection of AEs extends from the time the subject is administered study medication (Day 1) until Day 28 or early termination. Subjects with early termination will be followed up until Day 28. Follow-up of the AE, even after the date of therapy discontinuation, is required if the AE persists until the event resolves or stabilizes at a level acceptable to the investigator.

When changes in the intensity of an AE occur more frequently than once a day, the maximum intensity for the event should be noted. If the intensity category changes over a number of days, then those changes should be recorded separately (with distinct onset dates).

Specific guidelines for classifying AEs by intensity and relationship to study drug are given in [Table 3](#) and [Table 4](#).

Table 3. Classification of Adverse Events by Intensity

MILD: An event that is easily tolerated by the subject, causing minimal discomfort and not interfering with everyday activities.

MODERATE: An event that is sufficiently discomforting to interfere with normal everyday activities.

SEVERE: An event that prevents normal everyday activities.

Table 4. Classification of Adverse Events by Relationship to Study Drug

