12.4.2 Serious Adverse Events

In general for any clinical trial an SAE is any untoward medical occurrence, in the view of either the investigator or Sponsor, that:

- results in death,
- is life-threatening,
- results in inpatient hospitalization or prolongation of existing hospitalization,
- results in persistent or significant disability/incapacity, and/or
- is a congenital anomaly/birth defect

For the purposes of this study, death and inpatient hospitalization will not be considered as an SAE, as the primary end point of this study is the proportion of subjects requiring COVID-19 related hospitalization (including emergency room visit) or who die due to any cause within 28 days of randomization

Other important non-COVID-19 medical events that may not be immediately life-threatening or result in death or hospitalization, based upon appropriate medical judgment, are considered SAEs if they are thought to jeopardize the subject and/or require medical or surgical intervention to prevent one of the outcomes defining an SAE. SAEs are critically important for the identification of significant safety problems; therefore, it is important to take into account both the investigator's and the Sponsor's assessment. If either the Sponsor or the investigator believes that an event is serious, the event must be considered serious and evaluated by the Sponsor for expedited reporting.

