1 PURPOSE AND SCOPE OF STATISTICAL ANALYSIS PLAN

The purpose of this Statistical Analysis Plan (SAP) is to provide details regarding the analyses sets, endpoints, and statistical analysis methods to be used to meet the objectives of the NI03-CV19-001 trial. When differences exist in descriptions or explanations provided in the Clinical Study Protocol and this SAP, the SAP prevails. This SAP will be finalized prior to unblinding of the treatment allocations codes.

This document is designed to be a stand-alone document in terms of conveying essential statistical approaches to the analysis of the data. More definitions and details regarding variables collected are provided in the Clinical Study Protocol (version 4.0 at time of writing).

Statistical approaches were developed to be consistent with accepted statistical and clinical trial principles including ICH E9, Statistical principals for clinical trials¹.

¹ ICH E9 Expert Working Group. Statistical Principles for Clinical Trials: ICH Harmonized Tripartite Guideline. *Statistics in Medicine* 1999; 18:1905–1942.

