2.3.3 Safety/Tolerability

- Incidence of AEs and SAEs of any grade from randomization up to Day 28.

- Cumulative incidence of grade 3 and 4 AEs from randomization up to Day 28.
- Incidence of discontinuation from study due to an AE/SAE (discontinued subjects will be followed up until Day 28).
- Change from baseline in clinical laboratory parameters (including platelet counts, liver function tests, and potassium levels, etc.).
- Change from baseline in vital signs (heart rate, blood pressure, peripheral capillary oxygen saturation [SpO₂]).

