3.1 PRIMARY ANALYSIS

Disease Progression (Hospitalization): The Primary Efficacy Endpoint is defined as status changing from ambulatory care to COVID-19 related hospitalization, ER visit, or death due to any cause on or prior to Day 28. Presenting to the emergency room is considered hospitalization. Hospitalization/ER visit and Death are recorded on the End of Study (EOS) form and will support the primary endpoint analysis. All subjects who have an End of Study form with any Hospitalization/ER Visit or Death are assumed to be COVID-related and therefore analyzed as a failure of the primary endpoint. Subjects failing the primary endpoint will be described within the Clinical Study Report.

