4.3.1 Summary of Adverse Events

All analyses of adverse events will be based on the Safety Population. A summary of the numbers and percentages of patients within each treatment group experiencing at least one treatment emergent-adverse event (TEAE) will be provided in tables. A treatment emergent-adverse event is any AE that occurs after any exposure to treatment.

A Relative Risk comparison of the incidence in Camostat mesilate to Placebo will also be provided including a 95% Binomial Exact Confidence Interval when at least 3 subjects in both groups experienced the event.

TEAEs will be defined as an AE occurring from Day 1 to end of study which is defined as Day 28. 'Drug-related' is defined as 'possibly,' 'probably,' or 'definitely' caused by the study medication.

The AE endpoints summarized in this table are:

- With one or more TEAE
- With one or more drug-related TEAE
- With one or more serious TEAEs
- With one or more serious drug-related TEAE
- With one or more severe TEAE
- With one or more moderate or severe TEAE
- TEAE with outcome of death
- TEAE with outcome of drug related death
- Discontinued study drug due to AE/SAE
- Discontinued from study due to AE/SAE

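### SAP 4.3 limits the SAE summaries to non-COVID events, although the safety endpoint has no restriction by cause and no rule says how COVID-relatedness of an SAE is decided

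*SAP*

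**What the plan says.** The endpoint is set in Protocol 6.2.2 and repeated in SAP 2.3.3: "Incidence of AEs and SAEs of any grade from randomization up to Day 28". Neither place limits it by cause.

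SAP 4.3 contains two adjacent sentences. The first brings the gravest events into the data: "All adverse events that lead to death or are life threatening will be recorded as Serious Adverse Events in the SDTM datasets". The second limits what is tabulated: "Only non-COVID related Serious Adverse Event (SAE's) will be included in the summaries provided below". The summaries that follow, in SAP 4.3.1 and 4.3.2, include serious TEAEs, serious drug-related TEAEs, TEAEs with a fatal outcome, and a row for "TEAE with outcome of drug related death".

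Three other provisions bear on the point:

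- Protocol 12.4.2: "For the purposes of this study, death and inpatient hospitalization will not be considered as an SAE".
- SAP 3.1, on the primary endpoint: "All subjects who have an End of Study form with any Hospitalization/ER Visit or Death are assumed to be COVID-related".
- Protocol 12.4.1, on what is documented for each AE: "date of onset, duration, frequency, severity, relationship to study drug, action taken with study drug, treatment of event, and outcome". Relationship to study drug is in that list; relationship to COVID-19 is not.

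Where the two documents differ, SAP section 1 settles the order: "When differences exist in descriptions or explanations provided in the Clinical Study Protocol and this SAP, the SAP prevails".

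**The concern.** In a placebo-controlled trial, randomization lets the arms be compared on all serious events without anyone judging the cause of a single case. A filter on judged cause gives that up for the events it removes. If a serious drug reaction is read as COVID-19, it leaves the SAE tables. Some confusion is possible: Protocol 5.1.1 describes dyspnea and nausea in COVID-19, while Protocol 5.3 lists dyspnea among the first symptoms of shock or anaphylaxis and nausea among those of hepatic disorder on camostat.

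The secondary objective is the safety profile. The SAE tables as written would answer a narrower question than the declared endpoint, and a reader of those tables could not tell how many serious events were set aside in each arm, or why.

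**Working it through.** The documents give no expected number of SAEs, so the check is to set the provisions side by side.

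1. **Endpoint against tables.** SAP 2.3.3 covers SAEs of any cause; the SAP 4.3 summaries cover non-COVID SAEs only. Both statements are in the SAP, so the rule that the SAP prevails over the protocol does not settle the difference. Tables built to SAP 4.3 do not report the endpoint in SAP 2.3.3.

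2. **Which events are affected.** Protocol 12.4.2 takes death and inpatient hospitalization out of the SAE definition. SAP 4.3 puts AEs that lead to death back in as SAEs in SDTM, together with life-threatening ones, and the SAP prevails. It does not mention hospitalization. An ER visit alone is not a listed SAE criterion. The gravest events that the filter can remove are therefore fatal and life-threatening AEs labelled COVID-related.

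3. **How the label is assigned.** SAP 4.3 gives no definition, decision-maker or timing, and the AE items listed in Protocol 12.4.1 do not include it. There are two possibilities.
   - *Case-by-case judgement.* Non-COVID fatal and life-threatening SAEs stay in the tables, and COVID-labelled ones leave. Nothing says which label governs an event judged possibly drug-related and also COVID-related, so even the drug-related death row depends on an undefined rule.
   - *The SAP 3.1 assumption carried over.* Every death on the End of Study form would count as COVID-related, and the rows for TEAEs with outcome of death and drug-related death would be empty for those deaths.

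4. **What is compared elsewhere.** The composite of hospitalization, ER visit or death (SAP 4.1.1), time to that event (SAP 4.2.2) and survival at Days 15 and 28 (SAP 4.2.1) are compared by arm. The table list in the SAP appendix includes a listing of deaths in the Safety Population. SAP 4.3 lists all AEs by subject.

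5. **What remains uncovered.**
   - The efficacy analyses carry no system organ class or preferred term, so a net reduction in the composite could hide an excess of one kind of serious event.
   - The ITT analysis is by assignment (SAP 2.5.1), the Safety Population by treatment received (SAP 2.5.4). PP1 also goes by treatment received, but only in subjects who complete 14 days with 80% compliance (SAP 2.5.2).
   - A life-threatening event labelled COVID-related, without admission, ER visit or death, would enter neither the composite nor the SAE tables.
   - The severity tables are not a sure substitute. SAP 4.3 plans grade 3 to 5 TEAEs, but the table list limits Table 14.3.1.8 to non-serious grade 3 or 4 events, while its shell covers grades 3 to 5 without that limit.

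**The case against.** The strongest reply is that these outcomes are the efficacy endpoint. A drug that worsened the disease enough to cause admission or death would show in the primary, time-to-event and survival analyses; SAP 3.1 also promises a description of each primary failure in the study report. ALT, AST, alkaline phosphatase, GGT, potassium and platelets are summarized by arm with no COVID filter, so the hepatic, potassium and platelet reactions in Protocol 5.3 would largely remain visible. Protocol 5.3 also says that most anaphylactic symptoms arose within 30 minutes of dosing, which helps to tell them from the disease. All of this stands. It rules out the claim that serious outcomes vanish from comparison, but it does not supply an all-cause SAE table by event term and treatment received.

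A second reply is that a rule may exist outside these documents. The eCRF and the SAE reporting form are not included, so a COVID-relatedness field cannot be excluded. That is fair, but the SAP should still state the rule. The shell notes for Tables 14.3.1.5 and 14.3.1.7 do not repeat the non-COVID condition. That leaves the programmer with two instructions, since the shells are stated to be subject to revision and the restriction stands in the SAP text.

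A reader might also infer that SAP 3.1 already classifies every death as COVID-related for safety. The documents do not say so: that assumption is written for failure of the primary endpoint, and SAP 4.3 does not refer to it.

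**Conclusion.** The concern holds in a limited form. On any reading, COVID-labelled SAEs, fatal ones included, are left out of the SAE summaries, against the plan's own endpoint and without a stated rule. What is lost is the all-cause by-arm comparison of SAEs and deaths by system organ class, preferred term and treatment received. Empty death rows follow only if the SAP 3.1 assumption is carried into the safety tables.

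The loss cannot be expressed as a number from the documents. A reader might take the planning rates as its size: 186 × 0.15 = 27.9 and 93 × 0.30 = 27.9, which reproduces the nearly 28 per arm in SAP 4.1.3, or 200 × 0.15 = 30 and 100 × 0.30 = 30 at full enrolment. That is not supported. These are subjects with a hospitalization, ER visit or death, not SAEs. Hospitalization is removed as an SAE criterion by Protocol 12.4.2, and an ER visit alone was never one, so those events would be absent from the SAE tables even without the SAP 4.3 restriction. The number actually affected is the number of fatal and life-threatening AEs, and any other SAE, that receive the COVID label; the plan gives no figure for it.

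**What to change.** Before unblinding:

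- In SAP 4.3, 4.3.1 and 4.3.2 and Tables 14.3.1.1, 14.3.1.5 and 14.3.1.7, summarize all treatment-emergent SAEs and deaths by arm in the Safety Population, regardless of cause.
- Show the non-COVID subset as an additional row. State who classifies an SAE as COVID-related, on what criteria, and that this is done blinded.
- State that the SAP 3.1 assumption applies to the primary endpoint and does not govern the safety tables.
- Reconcile Protocol 12.4.2, SAP 3.1, SAP 4.3, SAP 4.3.1 and the table list on which deaths and hospitalizations count as SAEs, and align the list entry and shell for Table 14.3.1.8.

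The cost is SAP wording and one row per table. Fatal and life-threatening AEs are already to be held as SAEs in SDTM, so those rows need no new data. Hospitalizations and ER visits are recorded on the End of Study form, so whether they appear in SAE tables depends on the reconciliation. The downside is that disease events add some noise to the all-cause rows; the subset row lets a reader see past it.

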4.3.1 Summary of Adverse Events

All analyses of adverse events will be based on the Safety Population. A summary of the numbers and percentages of patients within each treatment group experiencing at least one treatment emergent-adverse event (TEAE) will be provided in tables. A treatment emergent-adverse event is any AE that occurs after any exposure to treatment.

A Relative Risk comparison of the incidence in Camostat mesilate to Placebo will also be provided including a 95% Binomial Exact Confidence Interval when at least 3 subjects in both groups experienced the event.

TEAEs will be defined as an AE occurring from Day 1 to end of study which is defined as Day 28. 'Drug-related' is defined as 'possibly,' 'probably,' or 'definitely' caused by the study medication.

The AE endpoints summarized in this table are:

- With one or more TEAE
- With one or more drug-related TEAE
- With one or more serious TEAEs
- With one or more serious drug-related TEAE
- With one or more severe TEAE
- With one or more moderate or severe TEAE
- TEAE with outcome of death
- TEAE with outcome of drug related death
- Discontinued study drug due to AE/SAE
- Discontinued from study due to AE/SAE

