Serious decreased platelets have been reported from post-marketing surveillance. Symptoms included subcutaneous hemorrhage, oral hemorrhage, and epistaxis. The number of days until the onset was within 1 month after administration in most cases. Possible idiopathic thrombocytopenic purpura was suspected in some reported cases. In subacute and chronic toxicity studies of the drug, the decrease in platelets was not observed, and the mechanism of pathogenesis remains unknown.

Hepatic Function Disorder, Jaundice

Hepatic function disorder and jaundice (both with unknown frequency), accompanied by extreme elevation of aspartate aminotransferase (AST), alanine aminotransferase (ALT), and gamma-glutamyl transferase (GGT), and alkaline phosphatase (ALP) have been reported from post-marketing surveillance. Initial symptoms included general fatigue, nausea and vomiting, and jaundice. Most of disorders occurred without subjective symptoms and identified by medical examinations. The duration from the beginning of dosage to onset was 12 months in many cases. Some disorders occurred (identified) after the end of administration of the drug. In subacute and chronic toxicity studies of the drug, hepatic function abnormal was not observed, and the mechanism of pathogenesis remains unknown.

Hyperkalemia

Serious hyperkalemia has been reported from post-marketing surveillance, although the frequency is unknown due to spontaneous reporting. Most of the disorders occurred without subjective symptoms and were identified by medical examinations. Abnormal electrocardiograms or electrocardiogram abnormalities with clinical symptoms (general fatigue and sensation of heaviness in chest) were observed in some cases. The duration from the beginning of dosage to the onset was within 2 months in most cases. In subacute and chronic toxicity studies of the drug, abnormal changes in potassium levels were not observed, and the mechanism of pathogenesis remains unknown.

Overall, the evidence of clinical activity and the AE profile observed support a positive benefit-to-risk ratio for subjects with COVID-19 who are treated with camostat mesilate.

Details regarding known or anticipated benefits and risks, as well as reasonably anticipated AEs for camostat mesilate may be found in the IB ([Sagent Pharmaceuticals, 2020](#)).

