4.3.2 Specific Adverse Events

The incidence rates (%) and event counts of TEAEs by system organ class (SOC) and by preferred term (PT) will be summarized by treatment group. The table will be organized

so that adverse event categories (SOC) are reported in upper case letters and specific adverse events (PT) are reported in lowercase.

The incidence rates (%) and event counts of TEAEs by system organ class (SOC) and by preferred term (PT) will be summarized by treatment group restricted to events with at least 5% incidence in either group.

Tables will summarize the incidence rates (%) of specific TEAE PTs, sorted by descending incidence of PT in the active drug group.

The incidence rates (%) and event counts of drug related TEAEs by SOC and by PT will be summarized by treatment group.

The incidence rates (%) and event counts of serious drug related TEAEs by SOC and by PT will be summarized by treatment group.

Tables will summarize the incidence rates (%) of serious TEAE PTs, sorted by descending incidence of PT in the active drug group.

The incidence rates (%) and event counts of serious drug related TEAEs by SOC and by PT will be summarized by treatment group.

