4.3.5 Safety Listings

A comprehensive set of safety listings will be provided for all subjects in the Safety Analysis Set. Adverse event listings will include SOC, PT, relationship, severity, onset and resolution dates (and study days), and action taken.

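### The relative-risk interval for adverse events needs at least 3 affected subjects in both arms, so a one-sided excess in a rare summary category gets counts but no interval

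*SAP*

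**What the plan says.** SAP 4.3.1 covers one summary table with ten categories, from any treatment-emergent adverse event (TEAE) down to serious drug-related events, deaths, drug-related deaths and discontinuations. The base display has no minimum count: "A summary of the numbers and percentages of patients within each treatment group experiencing at least one treatment emergent-adverse event (TEAE) will be provided". It then adds a comparison: "A Relative Risk comparison of the incidence in Camostat mesilate to Placebo will also be provided". The same sentence goes on to set a condition: "including a 95% Binomial Exact Confidence Interval when at least 3 subjects in both groups experienced the event". The text does not settle whether the condition governs the interval alone or the whole relative risk.

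SAP 4.3.2 gives by-arm tables at term level: "The incidence rates (%) and event counts of TEAEs by system organ class (SOC) and by preferred term (PT) will be summarized by treatment group". One of them is "restricted to events with at least 5% incidence in either group", so there the authors used an either-arm rule. SAP 4.3.2 does not call for a relative risk by preferred term. SAP 4.3.5 adds listings: "A comprehensive set of safety listings will be provided for all subjects in the Safety Analysis Set".

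SAP 4.3 narrows the serious events that are counted: "Only non-COVID related Serious Adverse Event (SAE's) will be included in the summaries provided below". Nowhere in SAP 4.3 to 4.3.5 is another between-arm measure planned for adverse events, neither a risk difference nor a test. Draft Table 14.3.1.1 has n and % for each arm and no column for a relative risk or an interval.

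**The concern.** Safety is the only stated secondary objective (Protocol 6.1.2, SAP 2.1.2), and the relative risk is the only planned between-arm measure for adverse events. A drug reaction typically shows as an event seen on drug and seldom on placebo. A rule that needs three affected subjects in both arms fails for that pattern and passes when both arms are similar. The 2:1 allocation makes this worse, because the smaller placebo arm has to reach a rate twice as high. At stake is whether the report gives a size and an uncertainty for a one-sided excess in the categories that matter most for safety, or leaves the reader with two bare counts.

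**Working it through.** **Inputs.** Arm sizes 200 and 100 and the 2:1 ratio are from SAP 2.4. The threshold of 3 in both groups is from SAP 4.3.1. Adverse-event rates are assumptions. Arm sizes assume that all 300 planned subjects are randomized and dosed.

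**1. The plan's own figure.** The display rule has no derived figure; the arm sizes do. Exact enumeration of Fisher's test at 15% versus 30%, two-sided 5%, gives 80.2% power at 183 + 92, which agrees with the 80% in Protocol 13.1. From SAP 4.1.4, 186 × 1.075 = 199.95 and 93 × 1.075 = 99.98, so 200 and 100 follow.

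**2. What the threshold means in each arm.** 3/200 = 1.5% of camostat; 3/100 = 3% of placebo.

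**3. Which results pass and fail.** Fisher p-values are two-sided and nominal, since the plan specifies no adverse-event test.

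| Camostat /200 | Placebo /100 | Fisher p | Meets rule |
|---|---|---|---|
| 9 | 0 | 0.032 | no |
| 10 | 0 | 0.034 | no |
| 16 | 1 | 0.015 | no |
| 20 | 2 | 0.010 | no |
| 2 | 8 | 0.003 | no |
| 6 | 3 | 1.0 | yes |
| 20 | 3 | 0.037 | yes |

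With no placebo events, 9 is the smallest camostat count with p < 0.05. The 2 versus 8 row shows that the rule is symmetric. The 20 versus 3 row shows that it does not block every excess.

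**4. How often the rule is met.** P(met) = P(X₁ ≥ 3) × P(X₀ ≥ 3), with X₁ ~ Bin(200, p₁) for camostat and X₀ ~ Bin(100, p₀) for placebo.

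For p₀ = 1%: P(X₀ ≥ 3) = 1 − 0.3660 − 0.3697 − 0.1849 = 0.0794. For p₁ = 8%, P(X₁ ≥ 3) is above 0.9999. The product is 7.9%.

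| Assumed placebo / camostat rate | 3 in both | 3 in either |
|---|---|---|
| 0.5% / 5% | 1.4% | 99.8% |
| 1% / 8% | 7.9% | > 99.9% |
| 2% / 10% | 32.3% | > 99.9% |

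The placebo factor alone is 88.2% at an assumed 5% placebo rate, so common categories are little affected.

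**5. Share of nominally significant camostat excesses left without an interval** (placebo / camostat rates assumed): 99.9% at 1% / 5%, 98.4% at 1% / 8%, 92.5% at 2% / 8% and 82.4% at 2% / 10%.

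**6. An interval is available for these results.** Take the Newcombe interval for the risk difference as an illustration. For 10/200 versus 0/100 the Wilson limits are 2.74% to 8.96% and 0 to 3.70%. The lower limit is 5.00 − √((5.00 − 2.74)² + 3.70²) = 5.00 − 4.34 = 0.7 points. The upper limit is 5.00 + (8.96 − 5.00) = 9.0 points. By the same method, 12 versus 0 gives +6.0 points (1.5 to 10.2) and 20 versus 2 gives +8.0 points (1.9 to 13.1).

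**The case against.** The strongest reply is that nothing is concealed. By-arm counts and percentages carry no minimum: the ten categories in SAP 4.3.1, all TEAEs by class and term in 4.3.2, severe events in 4.3.3 and listings in 4.3.5. A 10 versus 0 split would be printed. This stands. A reader might infer that the rule suppresses harm signals; the documents do not support that.

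Second, the scope is narrow. The sentence belongs to the summary categories, and no relative risk by preferred term is clearly planned. The broad categories should reach three placebo subjects easily. This also stands, and it limits the point to the rarer categories.

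Third, the condition may govern the interval only, so that the relative risk is still given wherever it is defined. That reading is open. The interval is lost on either reading, so the point survives.

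Fourth, a reader might cite the post-marketing risks in Protocol 5.3, for example "Serious hyperkalemia has been reported from post-marketing surveillance", as harms that the rule would hide. That does not follow. Potassium, platelets and the liver enzymes have their own by-arm summaries, shift tables and boxplots in the SAP table list, with no count threshold.

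Fifth, a relative risk is not finite with no placebo events, so some limit on the ratio is reasonable. True, but it does not justify a threshold of three in both arms, since a ratio exists with one or two placebo events and a risk difference exists at zero.

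Finally, safety reporting in a Phase 2 trial is descriptive, and an added effect measure may be called a matter of preference. That bears on priority. The SAP has already chosen to give a comparison, however, and the question is when it appears.

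**Conclusion.** The concern holds in limited form. In the rarer of the ten SAP 4.3.1 categories, the both-groups condition removes the confidence interval, and on one reading the relative risk, from one-sided results such as 10 versus 0 or 16 versus 1, and gives it for 6 versus 3. At assumed rates of 0.5% to 2% on placebo and 5% to 10% on camostat, the three pairs tabulated meet the rule in 1.4% to 32.3% of trials. These frequencies depend on the assumed rates and on 200 and 100 dosed subjects; that placebo is the limiting arm follows from the 2:1 allocation when its event rate is no higher than that on camostat.

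The loss is one of estimation, because the imbalance itself is tabulated and listed. Nor is the rule tilted only against detecting drug harm: it withholds placebo excesses in the same way, and it lets through large camostat excesses once placebo reaches three. The change is worth making before unblinding, because safety is a stated objective and no other between-arm measure would fill the gap.

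**What to change.** In SAP 4.3.1, for the ten summary categories:

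- Report the risk difference, camostat minus placebo, with an exact or Miettinen-Nurminen 95% CI when at least 3 subjects in either group had the event. This matches the either-group rule already used in SAP 4.3.2.
- Report the relative risk with its 95% CI when the placebo count is above zero, and reword the sentence so that it is clear what the condition governs.
- Add these columns to draft Table 14.3.1.1 and label the intervals as nominal.

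The cost is new text, a second interval method to program and a few more columns. No new data, visits or subjects are needed. Intervals in sparse categories will be wide and should be read as descriptive.
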